9 ETHICS

9.1 Institutional Review Board (IRB)/Ethics Committee (EC)

It is the responsibility of the investigator to have prospective approval of the study protocol, protocol amendments, ICFs, and other relevant documents, e.g., written subject instructions, recruitment advertisements, if applicable, from the IRB/EC before participation of human subjects in research studies. All correspondence with the IRB/EC should be retained in the Investigator Site File. Copies of IRB/EC approvals should be forwarded to the Sponsor.

All IRB/EC approvals should be signed by the IRB/EC chairperson or designee and must identify the IRB/EC name and address, the clinical protocol by title or protocol number or both, and the date approval or a favorable opinion was granted.

The Investigator is responsible for providing written summaries of the progress and status of the study at intervals not exceeding 1 year or otherwise specified by the IRB/EC. The Investigator must promptly supply the Sponsor or its designee, the IRB/EC, and, where applicable, the institution, with written reports on any changes significantly affecting the conduct of the study or increasing the risk to subjects.

9.2 Ethical Conduct of the Study

The study will be performed in accordance with the ethical principles that have their origin in the Declaration of Helsinki and all applicable regulations. In addition, the study will be conducted in accordance with the protocol, the International Conference on Harmonisation (ICH) tripartite guideline E6 (R2), Good Clinical Practice (GCP), and applicable local regulatory requirements and laws.

9.3 Subject Information and Consent

Written informed consents in compliance with US Title 21 Code of Federal Regulations (CFR) Part 50 shall be obtained from each subject before entering the study, upon re-screening, and when performing any unusual or non-routine procedure that involves risk to the subject. Informed consent templates may be provided by the Sponsor to investigative sites. If any institution-specific modifications to study-related procedures are proposed or made by the site, the consents should be reviewed by the Sponsor or its designee or both before IRB/EC submission. Once reviewed, the consents will be submitted by the Investigator to his or her IRB/EC for review and approval before the start of the study. If the ICF is revised during the course of the study, all active participating subjects must sign the revised form.

Before recruitment and enrollment, each prospective subject or his or her legal guardian will be given a full explanation of the study and be allowed to read the approved ICF. Once the Investigator is assured that the subject/legal guardian understands the implications of participating in the study, the subject/legal guardian will be asked to give consent to participate in the study by signing the ICF.

The Investigator shall retain the signed original ICF(s) and give a copy of the signed original form to the subject or legal guardian.

10 INVESTIGATOR'S OBLIGATIONS AND STUDY PERSONNEL

The study will be conducted by qualified investigators under the sponsorship of Palladio Biosciences, Inc. (the sponsor).

The contact information for the sponsor's Chief Medical Officer and the CRO's medical monitor are listed on the cover page of this protocol. Contact information for other sponsor personnel, ICON Clinical Research Limited, the designated CRO, and other vendors are listed in the Investigator Site File provided to each site.

The following administrative items are meant to guide the Investigator in the conduct of the study but may be subject to change based on industry and government standard operating procedures, working practice documents, or guidelines. Changes will be reported to the IRB but will not result in protocol amendments.

10.1 Confidentiality

All laboratory specimens, evaluation forms, reports, and other records will be identified in a manner designed to maintain subjects' confidentiality. All records will be kept in a secure storage area with limited access. Clinical information will not be released without subjects' (or legal guardians') written permission, except as necessary for monitoring and auditing by the Sponsor, its designee, the FDA, or the IRB/EC.

The Investigator and all employees and coworkers involved with this study may not disclose or use for any purpose other than performance of the study any data, record, or other unpublished, confidential information disclosed to those individuals for the purpose of the study. Prior written agreement from the Sponsor or its designee must be obtained for the disclosure of any said confidential information to other parties.

10.2 Financial Disclosure and Obligations

Investigators are required to provide financial disclosure information to allow the Sponsor to submit the complete and accurate certification or disclosure statements required under 21 CFR 54. In addition, the Investigator must provide to the Sponsor a commitment to promptly update this information if any relevant changes occur during the course of the investigation and for 1 year following the completion of the study.

Neither the Sponsor nor Sponsor's representatives is financially responsible for further testing or treatment of any medical condition that may be detected during the screening process. In addition, in the absence of specific arrangements, neither the Sponsor nor Sponsor's representatives is financially responsible for further treatment of the subject's disease.

10.3 Investigator Documentation

Before beginning the study, the Investigator will be asked to comply with ICH E6 (R2) [Section 10.4](#) and Title 21 of the CFR by providing the following essential documents, including but not limited to:

- IRB/EC written approval and any other local approval, as appropriate

- Original signed Investigator agreement page of the protocol
- Form FDA 1572, fully executed, and all updates on a new fully executed Form FDA 1572
- Curriculum vitae for the Investigator and each Sub-Investigator listed on Form FDA 1572
- Financial disclosure information to allow the Sponsor to submit complete and accurate certification or disclosure statements required under 21 CFR 54. In addition, the Investigators must provide to the Sponsor a commitment to promptly update this information if any relevant changes occur during the course of the investigation and for 1 year after the completion of the study.
- IRB/EC-approved informed consent, samples of site advertisements for recruitment for this study, and any other written information regarding this study that is to be provided to the subject or legal guardian, and
- Laboratory certifications and normal ranges for any local laboratories used by the site, in accordance with 42 CFR 493

10.4 Study Conduct

The Investigator agrees that the study will be conducted according to the principles of ICH E6 (R2). The Investigator will conduct all aspects of this study in accordance with all national, state, and local laws or regulations. Study information from this protocol will be posted on publicly available clinical trial registers before enrollment of subjects begins.

10.5 Adherence to Protocol

The Investigator agrees to conduct the study as outlined in this protocol in accordance with ICH E6 (R2) and all applicable guidelines and regulations.

10.6 Adverse Events and Study Report Requirements

By participating in this study, the Investigator agrees to submit reports of SAEs according to the timeline and method outlined in the protocol. In addition, the Investigator agrees to submit annual reports to the study site IRB as appropriate.

10.7 Investigator's Final Report

Upon completion of the study, the Investigator, where applicable, should inform the institution; the Investigator/institution should provide the IRB with a summary of the study's outcome and the Sponsor and regulatory authority with any reports required.

10.8 Records Retention

To enable evaluations and/or audits from regulatory authorities or the Sponsor, the investigator agrees to keep records, including the identity of all participating subjects (sufficient information to link records, e.g., eCRFs and hospital records), all original signed

ICFs, copies of all eCRFs, SAE forms, source documents, and detailed records of treatment disposition, and adequate documentation of relevant correspondence (e.g., letters, meeting minutes, telephone calls reports). The records should be retained by the investigator according to ICH, local regulations, or as specified in the Clinical Study Agreement, whichever is longer.

If the investigator becomes unable for any reason to continue to retain study records for the required period (e.g., retirement, relocation), the Sponsor should be prospectively notified. The study records must be transferred to a designee acceptable to the Sponsor, such as another investigator, another institution, or to the Sponsor. The investigator must obtain the Sponsor's written permission before disposing of any records, even if retention requirements have been met.

Essential documents should be retained until at least 2 years after the last approval of a marketing application in an ICH region and until there are no pending or contemplated marketing applications in an ICH region, or at least 2 years have elapsed since the formal discontinuation of clinical development of the study drug. These documents should be retained for a longer period, however, if required by the applicable regulatory requirements or by an agreement with the Sponsor. It is the responsibility of the Sponsor to inform the Investigator/institution as to when these documents no longer need to be retained.

10.9 Publications

After completion of the study, the data may be considered for reporting at a scientific meeting or for publication in a scientific journal. In these cases, the Sponsor will be responsible for these activities and will work with the Investigators to determine how the manuscript is written and edited, the number and order of authors, the publication to which it will be submitted, and other related issues. The Sponsor has final approval authority over all such issues.

Data are the property of the Sponsor and cannot be published without prior authorization from the Sponsor, but data and publication thereof will not be unduly withheld.

11 STUDY MANAGEMENT

11.1 Monitoring

11.1.1 Monitoring of the Study

The Clinical Monitor and/or designee, as a representative of the Sponsor, has the obligation to follow the study closely. In doing so, the Monitor will visit the Investigator and study site at periodic intervals, or conduct central or remote monitoring, in addition to maintaining necessary telephone, email and letter contact. The monitor will maintain current personal knowledge of the study through observation, review of study records and source documentation, and discussion of the conduct of the study with the Investigator and personnel.

All aspects of the study will be carefully monitored, by the Sponsor or its designee, for compliance with applicable government regulation with respect to current GCP and current standard operating procedures.

11.1.2 Inspection of Records and Quality Assurance

Investigators and institutions involved in the study will permit study-related monitoring, audits, IRB/EC review, and regulatory inspections by providing direct access to all study records. In the event of an audit or inspection, the Investigator agrees to allow the Sponsor, representatives of the Sponsor, or a regulatory agency (e.g., FDA or other regulatory agency) access to all study records.

It is important that the investigator(s) and their relevant personnel are available during the monitoring visits and possible audits or inspections and that sufficient time is devoted to the process.

The Investigator should promptly notify the Sponsor and/or its designee of any inspections scheduled by any regulatory authorities and promptly forward copies of any related reports received to the Sponsor.

11.2 Management of Protocol Amendments and Deviations

11.2.1 Modification of the Protocol

Any changes in this research activity, except those necessary to remove an apparent, immediate hazard to the subject, must be reviewed and approved by the Sponsor or its designee. Amendments to the protocol must be submitted in writing to the Investigator's IRB/EC for approval before subjects can be enrolled into an amended protocol, and before the changes can be implemented.

11.2.2 Protocol Deviations

The Investigator or designee must document and explain in the subject's source documentation any deviation from the approved protocol. The Investigator may implement a deviation from, or a change of, the protocol to eliminate an immediate hazard to study subjects without prior IRB/EC approval. As soon as possible after such an occurrence, the

implemented deviation or change, the reasons for it, and any proposed protocol amendments should be submitted to the IRB/EC for review and approval, to the Sponsor for agreement, and to the regulatory authorities, if required.

A protocol deviation is defined as an unintended or unanticipated departure from the procedures or processes approved by the Sponsor and the IRB and agreed to by the Investigator. A major deviation occurs when there is not adherence to the protocol by the subject or Investigator that results in a significant, additional risk to the subject. Major deviations can include not adhering to inclusion or exclusion criteria, enrollment of the subject without prior Sponsor approval, or not adhering to FDA regulations or ICH GCP guidelines, and will lead to the subject being withdrawn from the study ([Section 4.2](#)).

Protocol deviations will be documented by the Clinical Monitor throughout the course of monitoring visits. Investigators will be notified in writing by the monitor of deviations. The IRB/EC should be notified of all protocol deviations in a timely manner.

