4.2.3 Subject Withdrawal Criteria

A subject may withdraw from the study at any time at his/her own request or may be withdrawn at any time at the discretion of the Investigator for safety, behavioral, or administrative reasons.

Subjects who discontinue or are discontinued after the Baseline Period will be considered as a withdrawal, regardless of whether they have received study drug. A subject that withdraws from study drug will be treated as a study withdrawal unless they are being followed for safety reasons.

All premature discontinuations and their causes must be carefully documented in the eCRF, and in the AE form (if applicable).

Subjects not completing the entire study on study drug should be encouraged to continue with the visit schedule, a modified visit schedule, or telephone follow-up as agreed between the subject and the Investigator. At a minimum, subjects should be encouraged to complete the Early Termination Visit (Visit 24 – in the clinic) at the time of study drug discontinuation and the Follow-up Visits (Visits 25 – 27) over the 4 weeks after the last dose of study drug. Subjects with ongoing SAEs or AEs believed to be at least possibly related to study medication will continue to be followed until resolution or for 28 days as warranted by the nature of the AE. If the AE is related to abnormal liver chemistry test results, see [Section 7.3.7](#) for additional follow-up requirements.

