4.2.4 Reasons for Withdrawal

Reasons for withdrawal (subjects who refuse to return for any remaining study visits) or discontinuation (subjects who prematurely stop the treatment) at any time during the study may include, but are not limited, to the following:

1. No longer meet the protocol inclusion or exclusion criteria, e.g., require a prohibited concomitant medication.
2. Noncompliance with the protocol.
3. Lack of efficacy.
4. A serious or intolerable AE that, in the Investigator's opinion, requires withdrawal from the study, including but not limited to laboratory safety assessments that reveal clinically significant (CS) hematological or biochemical changes from the baseline values, other than changes that are expected for vasopressin antagonists, and symptoms of an intercurrent illness that justifies withdrawal. If the AE is related to abnormal liver chemistry test results, see [Section 7.3.7](#) for additional follow-up requirements. Mild elevations in serum creatinine or serum sodium are known pharmacodynamic effects of vasopressin antagonists like lixivaptan and are transient and reversible. Therefore, subjects should not be withdrawn from study participation solely due to mildly elevated serum creatinine or serum sodium. Cases where eGFR has declined by 25% or more from baseline should be discussed with the medical monitor and sponsor.
5. Death
6. Lost to follow-up.
7. Other (e.g., pregnancy, study burden, development of contraindication to use of study drug).
8. Withdrawal of consent (partial or complete).
9. Investigator's or Sponsor's decision to discontinue the subject's participation in the study.
10. Sponsor termination of the study.

Upon occurrence of an SAE or intolerable AE, the Investigator will confer with the medical monitor and Sponsor. If a subject is discontinued from study drug because of an AE, the

event will be followed until it is resolved or stable or up to 28 days as determined by the Investigator. Any subject may withdraw his or her consent at any time. Subjects' safety will be closely monitored throughout the study, and the study will be conducted following Good Clinical Practices (GCP). The entire study may be stopped at any time at the discretion of the Sponsor.

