4.2.6 Replacements

Subjects who withdraw from the study will not be replaced.

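### Protocol 11.2.2 mandates study withdrawal after a major deviation while Section 4.2 encourages continued visits, so follow-up of a dosed subject after such a withdrawal is not assured.

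*Protocol*

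**What the plan says.** **Protocol 11.2.2** states that major deviations can include not meeting the eligibility criteria, or "enrollment of the subject without prior Sponsor approval, or not adhering to FDA regulations or ICH GCP guidelines". It ends "and will lead to the subject being withdrawn from the study", with a cross-reference to Section 4.2. It makes no exception for subjects who have already been dosed.

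**Protocol 4.2.3** leaves withdrawal by the Investigator to discretion. It then says: "A subject that withdraws from study drug will be treated as a study withdrawal unless they are being followed for safety reasons". The same section says that subjects who do not complete the study on drug "should be encouraged to continue with the visit schedule, a modified visit schedule, or telephone follow-up", and at a minimum should be encouraged to attend the Early Termination visit (Visit 24) and Visits 25-27.

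**Protocol 4.2.4** separates "withdrawal (subjects who refuse to return for any remaining study visits) or discontinuation (subjects who prematurely stop the treatment". It lists loss of eligibility and noncompliance among reasons that may apply to either.

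**Protocol 4.2.6:** "Subjects who withdraw from the study will not be replaced".

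**Protocol 5.6** treats compliance below 80% as a significant deviation. It calls for notifying the sponsor and re-educating the subject, and says nothing of withdrawal. **SAP 6.6** puts the same shortfall on its list of major deviations.

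**SAP 8.2** tabulates study discontinuation and treatment discontinuation separately, each with its primary reason.

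**The concern.** The trial asks about hepatic safety in everyone who takes lixivaptan, with change in eGFR as the efficacy endpoint. Both need subjects to be observed after the event that ended their participation. In 11.2.2 the exit is mandatory, and it can be triggered by something the site did, such as enrolling without approval. The text that should say what happens next, Section 4.2, gives no single answer. A site could read 11.2.2 with the 4.2.4 definition and hold no further visits, or read it with the encouragement in 4.2.3 and hold all of them.

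The choice affects the analysis sets in different ways. Under protocol 8.2 and SAP 6.2 every dosed subject counts in the Safety Population, however short the observation. Under protocol 8.2 and SAP 6.3 the Efficacy Population needs at least one eGFR in the Follow-up Period. Site practice after a deviation would then help decide who contributes to the eGFR result.

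**Working it through.** The plan states no figure on this point. The sample size of up to 50 is set by analogy with another study, so there is no calculation to reproduce. The check is mainly a comparison of texts.

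**1. Is withdrawal mandatory?** 11.2.2: yes, for a major deviation. 4.2.3 and 4.2.4: no, the Investigator may withdraw a subject and the listed reasons may apply. These disagree.

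**2. What does withdrawal mean?** In 4.2.4 it means refusing the remaining visits. A subject removed under 11.2.2 has refused nothing, so the definition does not fit. In 4.2.3 stopping drug counts as withdrawal by default, which 4.2.4 would call discontinuation. These disagree.

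**3. What follow-up is assured?**
- 4.2.3 encourages the visit schedule, a modified schedule or telephone contact, with Visit 24/ET and Visits 25-27 as the encouraged minimum.
- 6.5.4 says final procedures and follow-up will be performed for subjects who terminate in Titration or Maintenance, but as 4.2.3 describes them. The obligation is therefore no firmer than 4.2.3.
- 4.2.5 requires every attempt to follow up withdrawn subjects. The steps it lists are calls, texts and a letter to learn why a subject did not return, not assessments.
- The safety exception in 4.2.3 is not defined. The rule that follows it covers ongoing SAEs and possibly related AEs. A subject with normal ALT and no such event is not clearly covered.

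**4. What is at risk for one subject?** From protocol Table 1, the closing visits hold two liver panels (Visit 24/ET and Visit 27) and three Follow-up creatinine values (Visits 25 and 26, and the chemistry panel at Visit 27). If none of the three is taken, the subject is outside the Efficacy Population.

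**5. The compliance rule.** SAP 6.6 makes compliance below 80% a major deviation, and 11.2.2 says a major deviation leads to withdrawal. Together they imply withdrawal. Protocol 5.6 says re-educate. These disagree.

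**6. Size, as illustration only.** The inputs below are assumptions: true event risk *p*, and *w* of 50 dosed subjects withdrawn after half of their risk was observed.

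Expected observed proportion = [(50 − w)p + 0.5wp] / 50 = p(1 − 0.5w/50)

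| w | Factor | p = 2% | p = 5% | p = 10% |
|---|---|---|---|---|
| 2 | 0.98 | 1.96% | 4.90% | 9.8% |
| 5 | 0.95 | 1.90% | 4.75% | 9.5% |
| 10 | 0.90 | 1.80% | 4.50% | 9.0% |

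The reported interval would not show the loss, because the denominator stays at 50. With no events the exact 95% upper limit is 1 − 0.025^(1/n). This gives 7.1% for n = 50, against 7.9% for n = 45 and 8.8% for n = 40 if only fully observed subjects counted. The table mixes lost treatment time with lost observation. Keeping the visits recovers only the second.

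**The case against.** The strongest reply is that 11.2.2 does not stand alone. It points to Section 4.2, which has a safety exception, encourages Visit 24/ET and Visits 25-27, and requires attempts to follow withdrawn subjects. Section 6.5.4 provides for final procedures, and values that are already elevated are retested under 7.3.7.1. A site can record the withdrawal and still hold the closing visits. This stands. A reader might infer that dosed subjects leave liver follow-up, and the documents do not support that. They support only that follow-up is not assured.

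A second reply concerns the endpoint. The primary endpoint needs an ALT rise that led to stopping the drug, and the hepatic secondary endpoints likewise need a resulting stop or dose reduction. An ALT rise that first appears after drug has stopped for a deviation cannot qualify. A reader might infer that primary events would be missed after withdrawal. By the endpoint's definition they would not. This also stands.

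Third, 11.2.2 defines a major deviation as non-adherence "that results in a significant, additional risk to the subject", and the listed items are what such deviations can include. It would be wrong to read the rule as catching every paperwork error. In addition, each subject has an eligibility review with the medical monitor before enrolment, which makes frequent entry errors less likely.

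Fourth, SAP 8.2 can still be produced, since 4.2.1 defines treatment completion and study completion separately. The default in 4.2.3 blurs the recording but does not defeat the table.

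None of these replies removes the disagreement between the sections or turns encouragement into a requirement.

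**Conclusion.** The point holds as an inconsistency with a limited consequence. Sections 11.2.2, 4.2.3 and 4.2.4 disagree on whether withdrawal is mandatory and on what it means, and SAP 6.6 read with 11.2.2 disagrees with protocol 5.6. A dosed subject withdrawn for a deviation remains in the Safety denominator, is not replaced, may miss the closing safety assessments, and is lost to the eGFR analysis if no Follow-up value is taken.

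The size cannot be derived. The documents give no rate or timing of major deviations, so a reader who assumes a rate and reports a percentage of subject-time lost has an assumption and not a finding. The 2% to 10% relative falls shown above depend wholly on 2 to 10 of 50 subjects being withdrawn halfway through their risk.

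The effect on this trial's reported results is small. SAP section 9 records early termination, with only 6 participants in the maintenance period and no statistical analyses. The point concerns the plan as written, and it is a cheap improvement more than a threat to the primary result.

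**What to change.** Reconcile protocol 11.2.2, 4.2.3, 4.2.4 and 5.6 with SAP 6.6 so that leaving observation and stopping study drug are separate events with separate definitions. Specifically:

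- State that a dosed subject with a major deviation remains in the assessments already scheduled, including Visit 24/ET and Visits 25-27, unless consent is withdrawn.
- Bring the 4.2.3 sentence on withdrawal from study drug into line with the 4.2.4 distinction.
- Record study discontinuation and treatment discontinuation separately, each with its reason, as SAP 8.2 tabulates them.
- Settle whether compliance below 80% is a major deviation for the purposes of 11.2.2, so that SAP 6.6 and protocol 5.6 lead to the same handling.

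Whether and when study drug stops after a deviation is for the sponsor to reconcile, and no rule is proposed here.

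The cost is a few sentences in a protocol amendment with a matching SAP edit, and the small expense of keeping already planned visits for the few subjects affected.
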